## 10.2 Baseline Values

Unless otherwise noted, baseline is defined as the last non-missing value recorded prior to the first application of study drug. If time is not recorded and the assessment was on the same day as the first application of study drug, then it will be assumed the assessment occurred prior to the application of study drug. If a subject was randomized but not treated, then baseline is defined as the last non-missing value on or before the date of randomization. For lesion counts, the in-clinic count will be used as baseline and sensitivity analyses on type of assessment may be performed.

## 10.3 Adjustments for Covariates

The model for the primary efficacy will include adjustments for the following covariates: investigator type (dermatologist vs other), household number of randomized subjects (1 subject per household vs 2 subjects per household), BOTE score at Baseline (no inflammation [BOTE=0] vs mild/moderate/severe/very severe inflammation [BOTE $\geq$ 1]), age (0 to <3, 3 to <4, 4 to <5, 5 to <6, 6 to <7, 8 to <9, 9 to <12, and  $\geq$ 12 years old), and baseline lesion count. If there are not at least 3 responders and non-responders at each level of the stratification factors, then that stratification factor will be removed from the model. If there are fewer than 10 responders/non-responders, then neither investigator type nor household number of randomized subjects nor BOTE score at Baseline will be included in the model.

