
2 INTRODUCTION

2.1 Background

Molluscum contagiosum (MC) is a common skin disorder that affects mainly healthy children (Dohil et al., 2006). MC has the greatest incidence in individuals aged 1–14 years (Schofield et al., 2011); prevalence in children is between 5% and 11% (FDA, 2020).

MC virus is an important human skin pathogen and can cause disfigurement and suffering in children. In adults, MC is less common and often sexually transmitted. Extensive and persistent skin infection with the virus can indicate underlying immunodeficiency. MC virus is distinct from other poxviruses because of its host and tissue adaptations. It infects only the skin and, rarely, the mucous membranes. The virus has developed efficient mechanisms to grow in differentiating cells of the human epidermis and is well adapted to human hosts (Chen et al., 2013).

Patients with atopic dermatitis (AD) have an impaired skin barrier in addition to immunological changes which could explain the rising prevalence and high number of lesions in this population. Topical corticosteroids and calcineurin inhibitors (both local immunosuppressants commonly applied to the skin in patients with atopic dermatitis) have been implicated as contributing factors in some patients (Olsen et al., 2014).

MC is transmitted between human hosts by the infectious matter discharged from the lesions. According to a prospective community cohort study (Olsen et al., 2015), the mean time to resolution was 13.3 months (SD 8.2). Eighty (30%) of 269 cases had not resolved by 18 months; 36 (13%) had not resolved by 24 months. Transmission to other children in the household occurred in 102 (41%) of 250 cases in the literature.

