6.7 Study Procedures by Time Point

6.7.1 Screening (Day –15 to Day 1) (In-Clinic Visit)

The following procedures must be performed and recorded at the Screening visit:

1. Review study procedures and information regarding the study including the potential risk and benefits of SB206 with the subject/caregiver and obtain documented consent/assent.
2. Obtain demographic information.
3. Obtain subject's medical history (including start date of the subject's current episode of molluscum [i.e., when molluscum was first noticed by the subject/caregiver]), household MC status, medication history, and concomitant medication information.
4. Perform lesion mapping and lesion count.

5. If applicable and visit is conducted in clinic, obtain UPT and evaluate results. If pregnancy test is positive, the subject may not participate in the study.
6. Review inclusion/exclusion to confirm whether subject qualifies to participate in the study.

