10.3 Testing Procedures

10.3.1 Analysis of the Primary Efficacy Endpoint

The primary efficacy endpoint for this study is the proportion of subjects achieving complete clearance of all treatable molluscum lesions at Week 12 for the ITT population. Complete clearance of all MC at Week 12 is defined as having a lesion count of 0 at Week 12. The number and percentage of subjects with complete clearance at Week 12 will be summarized by treatment group.

The primary efficacy endpoint will be analyzed using a generalized estimating equation (GEE) for logistic regression with an exchangeable working correlation structure. The model will include treatment, investigator type (dermatologist vs other), Baseline BOTE score (no inflammation (BOTE = 0) vs. mild/moderate/severe inflammation (BOTE \geq 1) and number of randomized subjects per household (1 subject per household vs. 2 subjects per household), age and Baseline lesion count as factors. The odds ratio between SB206 10.3% and vehicle gel, 95% CIs for the odds ratio, and P-value for the covariate-adjusted treatment comparison will be presented; together with predicted proportions along with their associated 95% confidence interval. Only subjects who achieve complete clearance at Week 12 will be counted as responders for the primary analysis. Subjects who discontinue the study before the Week 12 analysis visit for any reason will be considered not to have achieved complete clearance at Week 12, even if the subject discontinues after a lesion count of 0.

As a sensitivity analysis, the primary efficacy analysis will also be applied to the PP population. Additional sensitivity analyses may be performed including analyses that utilize alternative assumptions from those of this primary method to ensure that efficacy results are not driven by the method of handling missing data.

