### 9.3 Demographic and Baseline Characteristics

Demographic variables include age, sex, ethnicity, and race. Age will be calculated in years relative to the informed consent date.

Other baseline characteristics include lesion counts at baseline, site type (dermatologist vs other), number of sites and a breakdown of site type, number of randomly assigned subjects in household (1 subject vs 2 subjects), number of households and breakdown of household size, BOTE score at Baseline (no inflammation [BOTE=0] vs mild/moderate/severe/very severe inflammation [BOTE $\geq$ 1]), and age at and time since onset of symptoms of current molluscum episode. Descriptive statistics will be presented for ages and other continuous variables. Frequency counts and percentages will be presented for sex, ethnicity, race, and other categorical variables. Demographic and baseline characteristics will be summarized for the Safety, ITT, and PP Populations.

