## 10.6 Examination of Subgroups

Subgroup analyses of complete clearance at Week 12 for investigator type (dermatologist vs other), household number of randomized subjects (1 subject per household vs 2 subjects per household), and BOTE score at Baseline (no inflammation [BOTE=0] vs mild/moderate/severe/very severe inflammation [BOTE≥1]) will be presented in a forest plot for the ITT Population. An additional subgroup analysis of complete clearance at Week 12 for age

(<1 year old,  $\geq 1$  to <2 years old,  $\geq 2$  to <6 years old,  $\geq 6$  to <12 years old,  $\geq 12$  to <18 years old,  $\geq 18$  years old) and onset of MC symptoms duration prior to baseline ( $\leq 6$  months vs  $>6$  months) will be summarized descriptively for the ITT Population.

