#### **Stop Dates**

- If only the day of resolution is unknown, the day will be assumed to be the last day of the month (e.g., ??-JAN-2013 will be treated as 31-JAN-2013).
- If both the day and month of resolution are unknown, the event will be assumed to have ceased on the last day of the year (e.g., ??-???-2013 will be treated as 31-DEC-2013).
- If the stop date is completely missing and the event is not continuing, the event will be assumed to be after first application of study drug and will be imputed using the last known date on the study.

For the start dates of current molluscum episode and initial diagnosis, the day will be estimated as “01” if only day is missing. If both month and day are missing, then it will be estimated as “01-JUN-YYYY” or the subject’s date of birth, whichever is latest.

If the start date of current molluscum episode is partial, then the following imputation will be made:

- If only the day is unknown, the day will be assumed to be the first day of the month or the date of birth, whichever is later.
- If the day and month are missing, then the start date will be estimated to be June 1st or the date of birth, whichever is later.

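### The primary and responder-secondary models leave out time since onset of the current episode, a collected and plausibly prognostic baseline value, at a small cost in power

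*SAP*

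**What the plan says.** **Covariates.** SAP 10.3 opens with "The model for the primary efficacy will include adjustments for the following covariates" and names the three stratification factors, grouped age and baseline lesion count. SAP 11.1 repeats the set, and SAP 11.2 applies the same model to the three responder secondaries. Protocol 10.3.1 agrees: it adds "age and Baseline lesion count as factors" to the stratification factors.

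**Onset data.** Under Protocol 6.7.1 the Screening history includes the start date of the "current episode of molluscum [i.e., when molluscum was first noticed by the subject/caregiver", so it is a recalled date. SAP 9.3 tabulates "age at and time since onset of symptoms of current molluscum episode". The only planned efficacy use is in SAP 10.6, where clearance by "onset of MC symptoms duration prior to baseline" (at most 6 versus more than 6 months) is summarised descriptively.

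**Natural history.** Protocol 2.1 cites a community cohort in which "the mean time to resolution was 13.3 months (SD 8.2"). It adds: "Eighty (30%) of 269 cases had not resolved by 18 months; 36 (13%) had not resolved by 24 months".

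**Incomplete onset dates.** For the current episode, SAP Appendix A says: "If the day and month are missing, then the start date will be estimated to be June 1" (or the birth date if later). A missing day becomes the first of the month.

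Neither document says that duration is prognostic in trial subjects, gives its distribution, or explains why it is not a covariate.

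**The concern.** Molluscum clears by itself, so how far a child has progressed through the episode at entry should help to predict clearance over the next 12 weeks. The plan already accepts this reasoning. It adjusts for baseline BOTE, described as a sign of coming resolution, and for age and lesion count, which are not stratification factors. Time since onset is the obvious remaining measure of position in the disease course, and it is already collected.

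What is at stake is power for the primary test and the three responder secondaries, and some protection against chance imbalance in duration. The design has little slack. SAP 5 states 90% power and also reports 88% from its own simulation, and every secondary test depends on the primary result.

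**Working it through.** **1. The plan's power.** Inputs from SAP 5: 20% versus 29.5%, 425 per arm, two-sided 0.05.
- SE = √[(0.20×0.80 + 0.295×0.705)/425] = √(0.367975/425) = 0.02943.
- z = 0.095/0.02943 = 3.23. Power = Φ(3.23 − 1.96) = 89.8% (89.6% with pooled variance). The stated 90% is reproduced.

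**2. Do the cited figures imply that duration matters?** Assume that the cohort's times run from onset; the documents do not say.
- Mean hazard, months 0 to 18: −ln(80/269)/18 = 0.067 per month.
- Mean hazard, months 18 to 24: ln(80/36)/6 = 0.133 per month, about double.
- Twelve weeks is 84/30.4167 = 2.76 months. The 12-week clearance is 1 − exp(−0.0674×2.76) = 17.0% at the first rate and 1 − exp(−0.1331×2.76) = 30.8% at the second.
- Of the 80 unresolved at 18 months, 44 (55%) cleared by month 24. The earlier rate would give 1 − exp(−0.0674×6) = 33%.
- A constant (exponential) hazard would also need an SD equal to the mean, 13.3, not 8.2.

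**3. Size of the duration effect.** Fit a Weibull to mean 13.3 and SD 8.2: choose the shape c so that Γ(1+2/c)/Γ(1+1/c)² − 1 = (8.2/13.3)² = 0.380. Then p(t) = 1 − S(t+2.76)/S(t). The fit leaves 25% unresolved at 18 months and 11% at 24, against the 30% and 13% reported.

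| Months since onset | Weibull | Gamma |
|---|---|---|
| 3 | 12.7% | 12.8% |
| 6 | 17.6% | 19.4% |
| 12 | 25.0% | 26.8% |
| 18 | 30.8% | 30.7% |

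The trial's duration distribution is not given. With an assumed equilibrium distribution (density proportional to S(t), mean about 9.2 months), Weibull clearance averages 12% at or below 6 months and 26% above. The share of outcome variance explained, Var(p)/[p̄(1−p̄)], is about 4.5%. It is 4% to 5% across the Weibull and gamma fits, and 6% to 9% for a lognormal fit. A share of 4.5% is worth 850/(1−0.045) ≈ 890, or about 40 subjects.

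**4. Power with and without duration.** Simulated logistic regressions of 850 subjects with marginal rates fixed at 20% and 29.5% (4,000 trials; 3,000 in the last row). The model holds treatment only, or treatment and duration.

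| Assumed setting | Without | With log duration | With ≤6 / >6 months |
|---|---|---|---|
| Equilibrium | 89.7% | 90.8% | 90.4% |
| Exponential, mean 6 months | 90.5% | 91.8% | 91.7% |
| Equilibrium, logit effect doubled | 89.4% | 94.2% | 92.7% |
| Duration has no effect | 89.2% | 89.1% | 89.1% |

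The simulation error of a single power is √(0.9×0.1/4000) = 0.5 points. The with/without difference is firmer because both fits use the same trials, but its tenths are not exact. Further runs of the 6-month split with recall error, with and without a 5% missing category, put the gain at about 0.5 to 1.5 points.

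**5. Power, not a narrower interval.** In the equilibrium setting the log odds ratio moves from 0.516 to 0.543 and its SE rises from 0.162 to 0.166. The mean z goes from 0.516/0.162 = 3.19 to 0.543/0.166 = 3.27. The test gains although the SE does not shrink.

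**6. Missing onset dates.** The Appendix A rules for the episode start cover partial dates only. A wholly missing date leaves three options:
- *Drop the subject.* Missingness of about 4% to 5% cancels the base-case gain, and ITT subjects are lost.
- *Use the general start-date rule in Appendix A.* This can set the onset to the first application date, an extreme low value on a log scale. With 5% wholly missing (assumed), the simulated gain falls from about 1.2 points to between 0.0 and 0.5.
- *Add a missing category to the 6-month split.* Under the gamma fit with exponential durations of mean 6 and 9 months, power rises from 89.3% to 90.6% and from 89.4% to 90.7% with 5% missing. With 10% missing it rises from 89.6% to 90.7% and from 89.2% to 90.5%.

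**7. Chance imbalance.** Assume an even split and the 14-point clearance gap (26% − 12%). The SD of the between-arm difference in share is √(0.25×2/425) = 0.034. A 2-SD imbalance shifts the unadjusted difference by 0.069×14 ≈ 1 point of the 9.5 targeted.

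**The case against.** The strongest reply is that this is a covariate preference worth about one power point. Several parts of it stand.

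- **The comparator is thinner than the plan.** The simulations contain no BOTE, age or lesion count, and the planned model has all three. BOTE is itself a marker of imminent clearance. The gain beyond the planned model has not been estimated, and overlap would shrink it.
- **The prognostic evidence is indirect.** It rests on one cited cohort, an assumed time origin and an assumed distribution. SAP 5 draws on integrated NI-MC301 and NI-MC302 data, and we cannot see whether duration was examined there.
- **Duration is not ignored.** The baseline table would show an imbalance, and the subgroup summary shows clearance by duration.
- **The change is not free.** Onset is recalled, partial dates are imputed, wholly missing dates need a rule, and the protocol fixes the same covariate set.

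A reader might infer that the omission sacrifices precision, so that the odds-ratio interval is wider than it need be. Step 5 shows otherwise. A reader might also infer that the primary test is biased or invalid, or that the trial is underpowered. Randomisation protects the test whether or not duration is in the model, and the stated 90% is reproduced.

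The reply does not remove the point. The value is already collected, the protocol's own figures point to a rising clearance rate, and with no duration effect the simulated cost of including it is negligible (89.2% versus 89.1%).

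**Conclusion.** The omission is real, and its cost is small: roughly 0.5 to 1.5 points of power for the primary test under the assumed duration distributions. The responder secondaries use the same model, so a loss of the same kind applies there, but it was not computed. The loss is smaller if duration overlaps with BOTE, age or lesion count, and nil if duration does not predict clearance. The larger gain in the doubled-effect row is a sensitivity case that the cited figures do not support.

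The conclusion rests on three assumptions: the cohort's times run from onset, duration varies among trial subjects broadly as assumed, and recall is good enough to preserve much of the signal. It is a missed efficiency and not a validity defect. The documents do not show that duration is prognostic in this trial's subjects, only that it plausibly is. This is a cheap improvement of low priority.

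**What to change.** Before the Week 12 freeze and unblinding described in SAP 6:

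1. Add time since onset to SAP 10.3 and 11.1, for the primary and responder-secondary models, as at most 6 months, more than 6 months, or missing. This reuses the SAP 10.6 cut. Keep the Appendix A rules for partial dates. Send wholly missing dates to the missing category, so that no ITT subject is dropped and no onset is set to the first application date.
2. Say what happens if the missing category is sparse, for example by extending the SAP 10.3 rule on minimum responders and non-responders per level.
3. State whether duration carries over to the models that borrow the primary covariates (the Week 4 percent change in SAP 11.2 and the analyses in SAP 11.3). Align the covariate lists written out separately for multiple imputation (SAP 10.4) and for the one-subject-per-household analysis (SAP 11.1).
4. Record the departure from Protocol 10.3.1 in SAP 14, which now reports no changes.

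If onset was recorded in NI-MC301 and NI-MC302, the sponsor can first check there whether duration predicts clearance beyond BOTE, age and lesion count. If the primary model is to stay as it is, a pre-specified duration-adjusted supportive analysis is the minimum.

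The cost is one three-level covariate and a short SAP amendment, with no new data. The downside is small: recall error and imputed partial dates dilute the gain.

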## 10.4 Handling of Dropouts or Missing Data

In analyses based on response, a missing response will be considered a non-responder.

For a sensitivity analysis, subjects with missing lesion count at Week 12 but who demonstrated complete clearance at the last collected lesion assessment will be counted as responders.

An additional sensitivity analysis using multiple imputation will be performed to address subjects with missing lesion count at Week 12. A monotone imputation model will be utilized in the following steps:

1. The lesion count data will be imputed to follow a monotone missing data pattern using the Markov chain Monte Carlo method for 10 imputations.
2. Each of the 10 imputations will then be imputed a further 10 times using a monotone regression method to impute the remaining missing data and the Week 12 lesion count using lesion count assessments at Weeks 2, 4, and 8, treatment group, investigator type (dermatologist vs other), BOTE score at Baseline (no inflammation [BOTE=0] vs mild/moderate/severe/very severe inflammation [BOTE $\geq$ 1]), age (0 to <3, 3 to <4, 4 to <5, 5 to <6, 6 to <7, 8 to <9, 9 to <12, and  $\geq$ 12 years old), and baseline lesion count as covariates.

3. Complete Clearance at Week 12 will be re-derived based on the imputed values and then analyzed using the primary analysis model. The results of the 100 analyses will be transformed into a normal statistic and combined into a single analysis using PROC MIANALYZE.

The ROUND and MINIMUM options will be utilized in Steps 1 and 2 to ensure imputed values are non-negative integers. The seed to be used is 20200727.

For subjects with a missing lesion count at Week 12 and identified as “Lost to Follow-up” by the investigator, the following sensitivity analysis will be performed. These lost to follow-up subjects will be contacted to obtain a patient reported outcome of MC disease status at the end of their study participation of either ‘Resolved (no lesions left)’, ‘Resolving (number of lesions decreasing)’, ‘Unchanged (number of lesions similar to previous clinic visit)’, or ‘Worsening (number of lesions increased)’. A reported response endpoint will be derived in the following manner:

- If a subject has a Week 12 lesion count assessment, then the subject will be deemed a responder if the count was 0.
- If the subject did not have a Week 12 lesion count assessment and the response to the disease status was ‘Resolved (no lesions left)’ or ‘Resolving (number of lesions decreasing)’, then the subject will be deemed a responder.
- Otherwise, the subject will be deemed a non-responder.

The sensitivity analysis of this patient reported response will be analyzed in the same manner as the primary endpoint. A list of the patient reported outcome of MC disease status will be provided.

A sensitivity analysis on the manner of assessment of lesion counts at Week 12 (in-clinic vs. remote) may be performed where subjects with only a remote assessment will be counted as non-responders.

